14.4 Other Statistical Considerations

Analysis Data Sets

At a minimum, two distinct analysis sets will be used for the evaluation of primary and secondary effectiveness endpoints. The *intent-to-treat analysis* set will include all randomized patients enrolled in the study. The *per protocol analysis* set will only include patients with complete primary effectiveness endpoint data and no major protocol violations. The safety evaluation will be based on the intent-to-treat analysis set only.

Justification of Pooling Data across Centers

A formal analysis will be conducted to determine the appropriateness of pooling data across the study centers. This will include constructing a linear regression model for the primary effectiveness endpoint with three factors: center, treatment and center by treatment interaction. Furthermore, “super-centers” may be constructed from centers with small numbers of enrolled patients to be entered into models as fixed effects.

Verification of Randomization Procedure

In order to verify the success of the randomization procedure, the distribution of each baseline and demographic variable of interest will be summarized by treatment group. Continuous variables will be summarized via mean, median, standard deviation, and range. Categorical variables will be summarized via counts and frequency distributions.

Missing Data

A sensitivity analysis will be performed for each endpoint to assess the potential impact of missing data on the results. A detailed description of all planned sensitivity analyses can be found in the Statistical Analysis Plan together with the analysis of the relevant endpoints. Missing values will be ignored for the summaries of baseline characteristics, other summaries and safety endpoints.

Standard Statistical Methods

Unless otherwise stated, all *P*-values will be considered significant at a two-sided significance level of 0.05. Summary statistics will be generated for all relevant variables. In the comparison of continuous variables, distributions will be tested for the normality assumption. If standard parametric techniques are found to be inadequate, an appropriate non-parametric technique or a Box-Cox transformation will be used. No corrections will be made for multiple testing procedures. All analyses will be conducted using SAS® version 9.1 or higher.

15 Risk Analysis

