3.3.4 Randomization

Subjects will be randomized according to the pre-specified randomization schedule following the confirmation of enrollment eligibility. Subjects will be randomized to either the treatment or control arm in a 1:1 ratio. The randomization will be based on random, permuted blocks and stratified by center. Randomization will continue sequentially regardless of a subject not being treated according to their randomization assignment.

4 Study Objectives

This study is designed to evaluate the effect of using a POC combined with SOC long-term oxygen therapy versus SOC long-term oxygen therapy alone on the physical activity level of subjects with COPD requiring long-term oxygen therapy. This study will also assess the effect on oxygen usage, quality of life, hospitalizations, and death and the safety of the device.

5 Endpoints

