For exploratory endpoint 5, the baseline and week 12 follow-up visit values are the average value during the first and twelfth weeks of the study, respectively. For accuracy, only wear-filtered ActiGraph data will be used in the analysis.

Exploratory endpoints 2-5 will only be summarized with descriptive statistics and will not have formal hypothesis testing performed.

9 Analysis of Adverse Events

All adverse events occurring during the study will be summarized by type, seriousness, Investigator-reported relatedness (to the study procedure and the LTOT, POC, and ActiGraph devices), severity, and outcome with the number of events experienced and the number and percentage of subjects experiencing the event. Adverse events will also be summarized in a listing. No formal hypothesis testing will be performed.

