11.1 Analysis Sets

11.1.1 Intention-to-Treat

The intention-to-treat analysis set (ITT) consists of randomized subjects who begin long-term oxygen therapy, with or without a POC, receive an ActiGraph device, and have at least baseline ActiGraph data. The ITT analysis set will be used as the primary analysis set in analyzing all endpoints.

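### Safety is tied to the intent-to-treat set only, and no adverse event summary by actual POC exposure is planned, so non-use of the POC would dilute the POC-arm rates

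*Protocol*

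**What the plan says.** Protocol 14.4 names two analysis sets. The intent-to-treat "set will include all randomized patients enrolled in the study"; the per-protocol set is narrower. On safety it says: "The safety evaluation will be based on the intent-to-treat analysis set only".

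SAP 11.1.1 defines intention-to-treat as "randomized subjects who begin long-term oxygen therapy, with or without a POC, receive an ActiGraph device, and have at least baseline ActiGraph data", and adds: "The ITT analysis set will be used as the primary analysis set in analyzing all endpoints". SAP 11.1.2 reserves the per-protocol set for a secondary analysis of the primary endpoint. Neither document has a safety or as-treated set, or a rule for the arm under which an off-assignment patient's adverse events are reported.

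The aims in SAP section 4 extend to "hospitalizations, and death and the safety of the device". SAP 3.3.4 says: "Randomization will continue sequentially regardless of a subject not being treated according to their randomization assignment".

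SAP section 9 summarises adverse events "with the number of events experienced and the number and percentage of subjects experiencing the event". One of its summary dimensions is "Investigator-reported relatedness (to the study procedure and the LTOT, POC, and ActiGraph devices"). It adds a listing and plans no test. Protocol 14.3 attaches an exact binomial 95% upper bound to the frequency of each event type.

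Protocol 2.2 and SAP 3.2.2 bar control patients from using a POC. Neither document gives an expected rate of non-use in the POC arm or of POC use in the control arm.

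**The concern.** An adverse event percentage for a device is usually read as describing people exposed to it. Grouping by assigned arm is the right default for effectiveness, because dilution there works against a claim of benefit. For device harm, the same dilution pulls the arms together and lowers the apparent rate.

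Two routes are possible. A POC-arm patient who never uses the device cannot have a POC-caused event but still counts in the denominator. A control patient who obtains a POC can have such an event, and under the as-randomised convention it falls outside the POC-arm rate. At stake are the POC-arm percentages, their upper bounds, and the informal comparison with standard of care. Because no test is planned, those descriptive figures are the safety result.

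**Working it through.** The plan states no figure on this point, so there is none to reproduce. The check asks how far as-randomised grouping could move the reported rates.

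**Inputs.** From the documents: 95 patients per arm planned (SAP 3.1) and 109 enrolled in total at closure (SAP section 2). Assumed, because the documents give no values: u, the share of the POC arm that never uses the POC; c, the share of controls who use one; r, the risk of a POC-caused event in a user; and b, a background event risk that is the same in both arms.

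**Between-arm difference.**
- POC-arm rate = b + (1 − u)r
- SOC-arm rate = b + c·r
- Difference = r(1 − u − c), against a true excess of r

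The share of the excess that survives is 1 − u − c, whatever r is. With r = 10% and b = 0:

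| u | c | POC arm | SOC arm | Difference | Share kept |
|---|---|---|---|---|---|
| 0% | 0% | 10.0% | 0.0% | 10.0 points | 100% |
| 5% | 2% | 9.5% | 0.2% | 9.3 points | 93% |
| 10% | 5% | 9.0% | 0.5% | 8.5 points | 85% |
| 20% | 10% | 8.0% | 1.0% | 7.0 points | 70% |

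The last column restates the assumed u and c. It applies to POC-caused events only: background COPD events cancel in the difference and are not attenuated.

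**Events falling under SOC.** The expected number is 95 × c × r. For c = 2%, r = 5% this is 95 × 0.02 × 0.05 ≈ 0.1. For c = 10%, r = 20% it is 95 × 0.10 × 0.20 = 1.9. With about 54 per arm (roughly half of 109; the split is not given) the same extremes are 0.05 and 1.1. The control-arm route therefore moves few events.

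**Rate and upper bound in the POC arm.** Take 5 events, all in users, and read the protocol's bound as the one-sided 95% Clopper-Pearson limit, the 0.95 quantile of Beta(x + 1, n − x):

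| Denominator | Rate | Upper bound |
|---|---|---|
| 95, all randomised to POC | 5/95 = 5.3% | 10.7% |
| 86, users if u ≈ 10% | 5/86 = 5.8% | 11.8% |
| 76, users if u = 20% | 5/76 = 6.6% | 13.3% |

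This route needs no protocol breach by a control patient, only non-use in the POC arm.

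**The case against.** The case for leaving the plan alone has five parts.

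1. *The sentence concerns membership, not grouping.* In context it contrasts with the per-protocol set and stops randomised patients from being dropped from safety, which is protective. This stands. Neither document says under which arm an off-assignment event is tabulated, and SAP section 9 does not say its summaries are by arm. A reader might infer that the plan expressly counts a control patient's POC harm as a standard-of-care event. That follows from convention, not from the text.

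2. *POC-related events are already identified.* SAP section 9 summarises by relatedness to the POC specifically and adds a listing, so such an event is not lost in either arm. This stands in part. Relatedness is an unblinded investigator's judgement with an unknown category, some anticipated events are non-specific (headache is on both the COPD and the oxygen-therapy lists in Protocol 13.1.3), and neither output supplies the number of POC users as a denominator.

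3. *Crossover is unlikely.* Controls are barred from POCs, patients enter POC-naive, the devices need a prescription, and only the treatment arm is given one. SAP 3.3.4 is a rule about the allocation schedule; it forecasts no crossover. This stands for the control arm but does not address non-use in the POC arm. Protocol 14.3 allows POC-usage summaries, which could show non-use but would not link it to adverse events.

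4. *No safety test is planned, so no test is biased.* This is correct. The effect is on descriptive rates and bounds.

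5. *Grouping by exposure brings its own bias.* If never-users are sicker, for example after an early exacerbation or withdrawal, their events move to the unexposed column and the POC looks safer. This stands, and it is why an exposure table should supplement the assigned-arm table and not replace it.

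**Conclusion.** The point holds as a gap in the planned safety reporting. Safety is confined to the intent-to-treat set, and no treatment-received summary exists, despite a stated device-safety aim. Under the as-randomised reading, the POC-arm rate of POC-caused events is diluted by never-users, and the between-arm excess falls to (1 − u − c) of its true value.

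The size cannot be fixed from the documents. It is zero with full adherence and a 7% to 30% reduction over the ranges assumed above. A reader might infer that the device will be made to look safer by some such percentage; the documents do not support that, because they give no value for u, c or r and because the reduction applies only to POC-caused events. The result also assumes the same background risk in both arms. The remedy is a cheap supplementary table; the main safety analysis does not need to be replaced.

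**What to change.** - Keep the assigned-arm adverse event table as the main safety table, on all randomised patients as Protocol 14.4 defines them. State that set in SAP section 9 as well, because the SAP's own intention-to-treat definition also requires baseline activity-monitor data.
- In Protocol 14.4, delete the word "only" from the safety sentence.
- Add to Protocol 14.4 and SAP section 9, for example: *A supportive table will summarise adverse events by actual POC exposure (at least one recorded POC use versus none), with the number of POC users as the denominator for the exposed group.*
- Derive exposure from the POC-arm diaries (Protocol 9.5, SAP 3.2.4) and from Protocol Deviation eCRF records of any POC use by controls (Protocol 17.10). Diary entries for POC use are specified for the POC arm only, so control use rests mainly on deviation records; say so. Receipt of a study device cannot serve as the exposure definition, because every patient receives the activity monitor.
- Beside the table, state that it is not a randomised comparison and is open to selection, for example if never-users are sicker.

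The cost is a sentence or two in each document and one extra descriptive table from records the trial already keeps.

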7.1 Hypotheses

7.1.1 Continuous Secondary Endpoints

The null hypothesis for secondary endpoints 1-6 is that there is no difference in the endpoint means for the treatment and control arms (indicating equality). Rejection of the null hypothesis indicates the observed data supports the alternative hypothesis that a difference in the endpoint means exits between the treatment and control arms (indicating inequality). The hypotheses associated with these secondary endpoints are:

H₀:
$$\mu_t - \mu_c = 0$$

H₁: $\mu_t - \mu_c \neq 0$

where μ_t and μ_c are the endpoint means for the treatment and control arms, respectively.

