7.1.2 Categorical Secondary Endpoints

The null hypothesis for secondary endpoints 7 and 8 is that there is no difference in the endpoint proportions for the treatment and control arms (indicating equality). Rejection of the null hypothesis indicates the observed data supports the alternative hypothesis that a difference in the endpoint proportions exits between the treatment and control arms (indicating inequality). The hypotheses associated with these secondary endpoints are:

$$H_0$$
: $p_t - p_c = 0$
 H_1 : $p_t - p_c \neq 0$

where p_t and p_c are the endpoint proportions for the treatment and control arms, respectively.

8 Analysis of Exploratory Endpoints

The exploratory endpoints are evaluated at the week 12 follow-up visit and compare the treatment and control arms. Analysis of the exploratory endpoints evaluates the following:

- 1. Time from enrollment to hospitalization for a COPD or other respiratory condition-related inpatient hospitalization ≥ 24 hours
- 2. Number of days in hospital for COPD or other respiratory condition-related inpatient hospitalization ≥ 24 hours
- 3. All-cause unplanned hospitalizations
- 4. Change in average daily activity duration and intensity
- 5. Change in average energy expenditure/day

Exploratory endpoint 1 will be analyzed with a Cox proportional hazard model, using time to hospitalization as the response and treatment arm, center, age, and baseline 6MWT as predictors. The model will be summarized with regression coefficient estimates and standard deviations.

For exploratory endpoint 4, the baseline and week 12 follow-up visit values are the average value during the first and twelfth weeks of the study, respectively. For accuracy, only wake- and wear-filtered ActiGraph data will be used in the analysis. Exploratory endpoint 4 will be summarized in the following ways:

- Change in average duration per day at each intensity from baseline to the week 12 follow-up visit
- Average duration per day at each intensity over 12 weeks
- Change in percentage of time spent engaging in Sedentary to Very Low Physical Activity (SVLPA) from baseline to the week 12 follow-up visit

 Proportion of subjects engaging in Moderate to Vigorous Physical Activity (MVPA) at the week 12 follow-up visit who did not at baseline

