10.2 Hospital Anxiety and Depression Scale

The Hospital Anxiety and Depression Scale (HADS) is a commonly used, validated questionnaire that measures anxiety and depression (Stern, 2014). The HADS consists of 14 questions about how the subject has been feeling over a preceding period, three months for the purposes of this study, with 7 pertaining to anxiety and 7 to depression.

Each question has four possible answers corresponding to a score between 0 and 3 that are added together to get a total score. The total scores for anxiety and depression are determined separately and are classified as one of the following:

- 0-7: Normal
- 8-10: Borderline abnormal (borderline case)
- 11-21: Abnormal (case)

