10.4 St. George's Respiratory Questionnaire

The St. George's Respiratory Questionnaire (SGRQ) is a validated tool that can be used to measure health impairment in COPD patients. (Morishita-Katsu, et al., 2016). The SGRQ is a two-part questionnaire; Part 1 (questions 1-8) covers the patient's recollection of their symptoms over a preceding period, three months for the purposes of this study, and Part 2 (questions 9-16) addresses the patient's current state. The two parts are further categorized into three components: Symptoms (questions 1-8), Activity (questions 11 and 15), and Impacts (questions 9-10, 12-14, and 16-17).

Each possible answer for a question corresponds to a weight, between 0 and 100. The final score overall and for each component is the percentage of the total weight for selected answers out of the largest possible total weight for answers to the applicable questions. Higher final scores indicate more limitations.

11 General Statistical Considerations

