11.6 Data Summaries

Unless otherwise stated, data will be summarized as followed:

- Continuous variables will be summarized with the count, mean, standard deviation, median, and range. Hypothesis testing will use the t-test (or Wilcoxon rank-sum test).
- Categorical variables will be summarized with counts and percentages. Hypothesis testing will
 use the chi-squared test (or Fisher exact test).
- Level of significance (α) for statistical testing will be 0.05 and two-sided.

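### The eight secondary endpoints are formally tested at two-sided 0.05 with no correction, no gate on the primary and no statement that they are only supportive

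*Protocol*

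**What the plan says.** Protocol 14.4 sets the rule for all P-values: unless stated otherwise, they "will be considered significant at a two-sided significance level of 0.05". It then says "No corrections will be made for multiple testing procedures". SAP 11.6 keeps the same level, which "for statistical testing will be 0.05 and two-sided".

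SAP 7.1 makes the secondary endpoints inferential. In 7.1.1, "The null hypothesis for secondary endpoints 1-6 is that there is no difference in the endpoint means"; in 7.1.2, "The null hypothesis for secondary endpoints 7 and 8 is that there is no difference in the endpoint proportions". All eight numbered endpoints therefore have a formal test.

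Two of the instruments give more than one score. For HADS (SAP 10.2), "The total scores for anxiety and depression are determined separately". For SGRQ (SAP 10.4), "The final score overall and for each component is the percentage of the total weight" attached to the chosen answers, so there is one overall score and three component scores. Neither document says which of these scores are tested.

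The only conditional step is in Protocol 14.1. It concerns the primary PAL test itself, and its condition is only that PAL change has been assessed in both arms. By contrast, SAP section 8 makes exploratory endpoints 2 to 5 descriptive, and SAP section 9 does the same for adverse events.

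**The concern.** The SAP uses explicit wording where it wants no formal testing, and it does not use that wording for the secondary endpoints. They keep full hypotheses, the same 0.05 level as the primary, and no order of testing. Protocol 4.2 lists oxygen usage and quality of life beside physical activity as the main objectives, so a claim resting on either is foreseeable.

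This matters more because of the early closure. SAP section 2 reports 109 of 190 planned subjects enrolled, so the primary comparison can miss significance even if the planned effect is real. As written, the plan would then allow any secondary result below 0.05 to be called significant, with no limit on the error rate across the family.

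**Working it through.** **The plan's own figures.** The documents state no familywise error rate, so there is none to reproduce. The primary sample size does reproduce: difference 0.1, SD 0.22, two-sided 0.05 and 77 per arm give 80.0% power by the t-test.

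**Number of tests** (SAP 7, 10.2, 10.4)

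- Oxygen usage 1, 6MWT 1, exacerbations 1, hospitalization 1, steps 1: subtotal 5
- SGRQ total 1, HADS anxiety 1, HADS depression 1: subtotal 3
- Respiratory mortality 1, all-cause mortality 1: subtotal 2
- Total 5 + 3 + 2 = 10

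Testing the three SGRQ components as well would make 13, but the SAP gives only their scoring. Leaving out mortality makes 8.

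**Independent tests, all nulls true.** For k tests:

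- any false significant difference, either direction: 1 − 0.95^k
- any false difference favouring POC: 1 − 0.975^k, because a two-sided 0.05 test spends 0.025 in that direction

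For k = 10: 1 − 0.95^10 = 0.401 and 1 − 0.975^10 = 0.224. For k = 8: 1 − 0.95^8 = 0.337 and 1 − 0.975^8 = 0.183.

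**Correlated tests.** The documents give no correlations, so a common pairwise correlation ρ between normal test statistics is assumed. The probabilities come from simulation (400,000 draws), checked by numerical integration.

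| Tests | Direction | ρ = 0 | ρ = 0.3 | ρ = 0.5 | ρ = 0.7 |
|---|---|---|---|---|---|
| 10 | either | 40% | 35% | 29% | 21% |
| 10 | POC benefit | 22% | 18% | 14% | 11% |
| 8 (no mortality) | either | 34% | 30% | 25% | 19% |
| 8 (no mortality) | POC benefit | 18% | 15% | 12.5% | 9.5% |
| 13 (with SGRQ components) | either | 49% | 42% | 33% | 24% |
| 13 (with SGRQ components) | POC benefit | 28% | 21% | 17% | 12% |

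**Why the 8-test rows matter.** Mortality over 12 weeks is not given. Assuming 1% to 5% and about 54 per arm (109 / 2 = 54.5), the exact two-sided size of Fisher's test runs from below 0.001 to 0.009, not 0.05. These two tests add almost no error, so the realistic figure lies close to the 8-test rows.

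**Power of the primary after closure.** With the plan's difference and SD, 54.5 per arm gives 65% power if every subject is evaluable. With the planned 20% attrition, 54.5 × 0.8 = 43.6 per arm gives 56%.

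**The case against.** The strongest defence is that this is a post-approval study of cleared devices with one named primary endpoint. Study success is tied to PAL alone, and the Protocol uses the language of demonstration only for PAL. The lack of adjustment is stated openly, so an informed reader can discount the secondary p-values. Exploratory endpoints 2 to 5 and adverse events are already descriptive, and the SAP restricts the per-protocol set to the primary. All of this is correct, and it weighs against requiring a formal multiplicity procedure. It does not supply the missing statement: neither document says that secondary results are supportive, and Protocol 14.4 says that they may be called significant.

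A gate would also have a real cost. At 56% to 65% power, testing secondary endpoints only after the primary rejects would rule out all secondary testing in roughly 35% to 44% of trials even if the planned effect were real. That is a good reason to leave a gate optional.

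Two stronger readings are tempting, and the documents support neither. A reader might infer that a false POC benefit on at least one endpoint is likely. It is not: the 40% figure counts false differences in both directions, including harm, and the chance of a false benefit is 22% even under independence. Passing one half would take 28 independent tests (1 − 0.975^28 = 0.508). A reader might also take 13 as the settled count, but nothing in the SAP says that the SGRQ components have their own tests.

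The open-label design is a separate matter. Unblinded SGRQ, HADS and diary answers may be biased, but that does not enter this calculation, and no multiplicity procedure would remove it.

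**Conclusion.** The concern holds at moderate size. With about 10 tests and no true effects, the plan allows roughly a 40% chance of at least one false significant difference and a 22% chance of at least one false POC benefit if the tests are independent. At an assumed correlation of 0.5 these fall to 29% and 14%. Without the sparse mortality tests the pairs are 34% and 18% (independent) and 25% and 12.5% (correlation 0.5). The false-benefit figures are about 5 to 9 times the nominal 2.5% (12.5 / 2.5 = 5; 22.4 / 2.5 = 9).

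These figures rest on all nulls being true, on HADS being tested as two scores and SGRQ as one, and on an equal-correlation model chosen for illustration. Covariate-adjusted models under Protocol 14.3 could raise the count, and stronger correlation would lower the error. The fault is in what the plan lets the study conclude; the individual tests are not in question.

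**What to change.** In SAP section 7, and in place of the no-correction sentence in Protocol 14.4:

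- State that only the primary PAL comparison supports a confirmatory claim.
- Report each secondary endpoint as an estimate with a 95% confidence interval and a nominal, unadjusted p-value, without the words *significant* or *demonstrated*.
- Name the SGRQ total, HADS anxiety and HADS depression as the scores tested, and make the SGRQ components descriptive.

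A Holm procedure over the secondary family, opened only if the primary rejects in favour of POC, is an option for a sponsor that wants a formal secondary claim. It is not required.

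The cost is a few sentences, with no new data or visits. The study has already closed, so if the Protocol is not amended, the SAP should say that its statement replaces the one in Protocol 14.4. The downside is that no secondary result could be claimed as established on its own. The nominal label does not make a chance p-value below 0.05 any rarer; it limits what may be concluded from one.
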